## 7. Treatment and follow-up plan

- 7.1 All enrolled patients will receive AHCC or placebo 3g every day until disease progression, intolerance or patient or physician decision to discontinue.
- 7.2 During treatment the subjects will be followed according to the follow-up plan summarized in the following table:
  - 7.2.1 Hematology and biochemistry levels will be checked within 72 hours before each administration of study drug treatment.
  - 7.2.2 A window of +/- 7 calendar days is allowable for imaging examination for tumor assessment.
  - 7.3 Prohibited treatment during the study drug treatment period includes the following:
    - 7.3.1 Investigational agents for the treatment of cancer;

7.3.2 Systemic steroids > 10 mg within 14 days of dosing (with a few exceptions eg, steroids for adrenal insufficiency, steroids if taken as part of prophylaxis for CT prep).

	Screen	Treatment Cycles (21-day cycles)					End-of-treatment
	Screen						(EOT) evaluation a
		C1 C2		C3	C4	C5	4 weeks after last
Week		C6	C7	C8	C9	C10	treatment
		:	:	:	:	:	treatment
Informed consent	Х						
Inclusion/exclusion criteria	Х						
Demography/ tumour staging	X						
Medical history	X						
Vital signs	X	Х	Х	Х	Х	Х	X
ECG	X						X
Blood test b	Х		Х	Х	Χ	Χ	Х
Urinalysis	Х					Х	X
HBV/HCV serology markers c	Х						Х
Performance status	Х	Х	Х	Х	Χ	Х	X
Chest X-ray	Х						X
Tumor assessment d	Х					Χ	
Treatment		Х	Х	Х	Х	Х	
Pregnancy test e	Х						
lmmunological study f	Х					Х	Х
Thyroid function g	Х						Х
Tolerability/AE reporting		Χ	Χ	Χ	Х	Х	Х
QOL questionnaire	Х			Х		Χ	Х

- a) The EOT assessment will take place at approximately 1 month after last treatment.
- b) Blood tests will include CBC/DC, albumin, total and direct bilirubin, transaminases (AST and ALT), ALP, AC sugar, sodium, blood urea nitrogen (BUN), creatinine, amylase, lipase, Troponin-T(or hs-cTnT), pro-BNP (brain natriuretic peptide), and creatinine kinase (CK) or CK-MB isoform (CK-MB). Other biochemistry tests may be done at the discretion of individual investigators.

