## 8. Assessment of treatment efficacy and safety

- 8.1 Assessment of treatment efficacy
  - 8.1.1 All enrolled patients will receive assessment of tumor response by imaging studies every 12 weeks, according to RECIST version 1.1. Computed tomography is the preferred imaging modality and should include imaging of chest and abdomen at baseline and follow-up.
  - 8.1.2 For subjects who are considered suitable for surgical resection, the actual surgical procedure will be determined by individual treating surgeons and will be recorded. The time frame for holding the study drug prior to surgery will be determined by the treating physician. Participants may resume the study drug after recovery from surgery, at the physician's discretion.
- 8.2 Management of immune-related adverse events (irAE) 7,8
  - 8.2.1 The definition of the most irAE and according management recommendation are summarized in the following table.
  - 8.2.2 For the definition of hepatitis grading, only ALT (alanine aminotransferase) level is used because it is more specific to liver inflammation.
  - 8.2.3 Definition of study drug-induced liver injury (DILI) was listed below, according to the amendment #8 of the CA209040 protocol:
    - 8.2.3.1 Concurrent ALT  $\geq$  10 x ULN AND total bilirubin  $\geq$  2 x ULN or baseline value (if elevated bilirubin at study entry), AND
    - 8.2.3.2 No other immediately apparent possible causes of ALT elevation and hyperbilirubinemia, including, but not limited to, tumor progression, acute viral hepatitis, cholestasis, pre-existing hepatic disease or the administration of other drug(s), herbal medications and substances known to be hepatotoxic.
    - 8.2.3.3 Management of hepatic events, including dose delay and/or discontinuation as well as intervention with steroid treatment, will follow the recommendation listed below, will not be impacted by the definition of DILI.

Types of irAE	Grade 1	Grade 2	Grade 3	Grade 4

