Nephritis	Creatinine > 1X ULN and ≤1.5 X baseline; proteinuria 1+, <1.0g / 24 h:  • Monitor renal function weekly; hydration	Creatinine > 1.5–3.0 X baseline; proteinuria 2+, 1.0– 3.4 g/24 h: • Steroid treatment (e.g., prednisolone 0.5–1 mg/kg/day or IV equivalent) • Delay study drug administration. Monitor renal function every 2-3 days; If worsens, manage as per grade 3 • Exclude non-immune causes	Creatinine > 3.0 X baseline to ≤ 6X ULN; proteinuria ≥ 3.5 g/24 h:  • As per Grade 2  • Consider renal biopsy  • If elevations persist > 7 days or worsens, manage as per grade 4	Creatinine > 6.0 X ULN:  • Steroid treatment (e.g., prednisolone 1–2 mg/kg/day or IV equivalent)  • Consider renal biopsy • Discontinue study drug treatment
Skin rash	<10% BSA:	10–30% BSA:	>30% BSA:	Life threatening

Antihistamines and topical steroid for pruritus	
 
As per G1 if tolerable
 
If intolerable, steroid treatment (eg prednisolone 0.5–1 mg/kg/day with a 1–2 week wean)
 
Delay study drug treatment until G1 and steroids <10 mg/day
 
Consider skin biopsy if symptoms persist or recur
 
	
 
Consult dermatologist and consider skin biopsy
 
Steroid treatment (e.g., prednisolone 1 mg/kg/day or IV equivalent).
 
Delay study drug treatment until G1 and steroids <10 mg/day
 
	consequences • As per Grade 3.
---	---	--	--------------------------------

- 8.2.4 When irAE improved to Grade 1 after steroid treatment, may taper steroid dosage over at least 1 month.
- 8.2.5 For other grade 3-4 toxicities (according to CTCAE version 4) that are considered to be related to study drug treatment, study drug treatment should be held if the toxicities last for 3 days or more under best supportive care. Further study drug treatment may be considered when toxicity has resolved to ≤ grade 1, after discussion with the principal investigator.
- 8.2.6 Recent review of irAE indicated the clinical significance of the rare but potentially fatal cardiac toxicity for patients who received combination immunotherapy . Cardiac exam (echocardiography or radionuclide ventriculography (MUGA scan)) will be done at baseline, at the first imaging assessment, and at the end-of-treatment (EOT) evaluation. Troponin-T(or hs-cTnT), pro-BNP (brain natriuretic peptide), and creatinine kinase (CK) or CK-MB isoform (CK-MB) will be checked every 3 weeks before each administration of study drug treatment and at EOT evaluation.

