## 10. Criteria for discontinuation of study drug treatment

Discontinuation of study drug treatment is when a patient no longer receives study drug but continues to be followed up for tumor status and survival according to local treatment guidelines for up to half year, unless consent is withdrawn. Patients may be discontinued from study drug treatment and assessments at any time. When study drug treatment is discontinued due to the reasons listed below, no further AHCC/placebo treatment will be provided by this study and further anticancer therapy will be decided by the investigators according to current treatment guidelines. Specific reasons for discontinuation of study drug treatment include:

- 10.1 Voluntary discontinuation by the subject who is at any time free to discontinue his/her participation in this study, without prejudice to further treatment.
- 10.2 When the investigator(s) consider other treatment modalities (surgery, others) are more suitable for the subjects according to assessment of tumor response specified in the protocol.
- 10.3 Safety reasons as judged by the investigator. Severe non-compliance to protocol as judged by the investigator.
- 10.4 Incorrect enrollment, in the opinion of the investigator or study delivery team physician, which will compromise the patient's health if study drug treatment or assessments are continued.
- 10.5 Dose delay or interruption of study drug treatment for more than 3 weeks.

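### Protocol rules for holding, resuming and stopping study drug conflict in sections 7.3.2, 8.1.2, 8.2 and 10, and none is given precedence

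*Protocol*

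**What the plan says.** The relevant rules stand in four parts of the protocol.

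- **Dosing and prohibited treatment (section 7).** AHCC or placebo is taken daily (7.1). Section 7.3.2 prohibits "Systemic steroids > 10 mg within 14 days of dosing". It allows a few exceptions by way of example (adrenal insufficiency, CT preparation). Treatment of immune-related adverse events (irAEs) is not among the examples.
- **irAE management (section 8.2).** Grade 2 hepatitis: prednisolone 1-2 mg/kg/day if there is no improvement or worsening, with a 4-week taper and no instruction to hold study drug. Grade 3 hepatitis: delay below stated ALT and bilirubin limits, steroids, and otherwise as grade 2. Grade 2 diarrhoea: delay, with a 2-4 week taper if steroids are used. Grade 2 pneumonitis: delay, and possible continuation once symptoms have fully resolved. Rash: "Delay study drug treatment until G1 and steroids" are below 10 mg/day, with a 1-2 week wean at grade 2. Section 8.2.4 adds a general line: "When irAE improved to Grade 1 after steroid treatment, may taper steroid dosage over at least 1 month".
- **Surgery (section 8.1.2).** "The time frame for holding the study drug prior to surgery will be determined by the treating physician", and afterwards "Participants may resume the study drug after recovery from surgery, at the physician's discretion".
- **Discontinuation (section 10).** The listed reasons include 10.2, "When the investigator(s) consider other treatment modalities (surgery, others) are more suitable for the subjects", and "10.5 Dose delay or interruption of study drug treatment for more than 3 weeks". Once a listed reason applies, "no further AHCC/placebo treatment will be provided by this study".

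**The concern.** These rules decide when a participant is dosed, held, or permanently taken off the intervention, and in several situations they give different answers. One line allows dosing that another prohibits, or allows a return that another rules out. The protocol gives no order of precedence. Section 12.2 foresees more than one participating center, so two sites could treat the same situation differently and each cite the protocol.

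What is at stake is consistency of exposure. Tumor response is first assessed at 12 weeks, so an early irAE could end AHCC/placebo before the primary endpoint is first measured under one reading and not under another. The per-protocol population (11.4.2) requires at least 6 weeks of study medication, so membership could also turn on the reading chosen. The triggers, toxicity and resectability, arise after randomisation.

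**Working it through.** The plan gives no figure to reproduce. Two of the three conflicts follow from comparing the text; the other needs a comparison of durations.

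**1. Steroid prohibition against the irAE table (no arithmetic).**
- Under 7.3.2 a patient on more than 10 mg, or within 14 days of it, should not be dosed unless an exception applies. Under the grade 2 hepatitis row a patient may receive 1-2 mg/kg/day while daily study drug continues. At an assumed 60 kg that is 60-120 mg/day.
- The rash row lets study drug restart at grade 1 with steroids below 10 mg/day. Section 7.3.2 would add 14 days after the last dose above 10 mg.

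**2. Steroid-treated delays against the 3-week limit.**
Inputs from the protocol: limit 21 days (10.5); interval 14 days (7.3.2); taper lengths and starting doses from the irAE table and 8.2.4. Assumptions not in the protocol: linear taper to zero, body weight 60 kg (range 50-80 kg), 1 month = 30 days. Time at full dose before the taper is counted as zero, which favours feasibility.

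Day on which the dose reaches 10 mg = taper days × (1 − 10 / starting dose in mg). Earliest dosing under 7.3.2 = that day + 14.

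Example: 28 × (1 − 10/60) = 23.3; 28 × (1 − 10/120) = 25.7.

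| Taper | Start at 60 kg | Day 10 mg reached | Plus 14 days |
|---|---|---|---|
| Rash grade 2, 1 week | 30 / 60 mg | 4.7 / 5.8 | 18.7 / 19.8 |
| Rash or diarrhoea grade 2, 2 weeks | 30 / 60 mg | 9.3 / 11.7 | 23.3 / 25.7 |
| Diarrhoea grade 2, 4 weeks | 30 / 60 mg | 18.7 / 23.3 | 32.7 / 37.3 |
| Hepatitis, 4 weeks | 60 / 120 mg | 23.3 / 25.7 | 37.3 / 39.7 |
| 8.2.4, 30 days | 30 / 60 / 120 mg | 20.0 / 25.0 / 27.5 | 34.0 / 39.0 / 41.5 |

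Across 50-80 kg:
- The 4-week hepatitis taper reaches 10 mg on days 22.4-26.2, beyond 21 even before the 14 days, and allows dosing on days 36.4-40.2.
- The 30-day taper reaches 10 mg on days 18.0-28.1 and allows dosing on days 32.0-42.1, over the limit in every case.
- The 2-week taper fits within 21 days without the 14-day interval (days 8.4-12.2) and not with it (days 22.4-26.2).
- The 1-week wean fits even with the interval (days 18.2-20.1), provided almost no time is spent at full dose.

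**3. Surgery (no figure can be computed).**
Section 8.1.2 leaves both the pre-operative hold and the recovery period open, then allows a return to study drug. Section 10.2 makes a judgement that surgery is more suitable a reason for discontinuation, with no further AHCC/placebo. Section 10.5 separately ends treatment if hold plus recovery exceeds 3 weeks. A patient sent to resection can therefore fall under all three.

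**The case against.** The strongest reply is that a delay with a cap is not a contradiction: resume if the conditions are met within 3 weeks, otherwise stop. That stands as a general principle. A reader might infer that the delay-and-resume instructions cannot be carried out at all. The protocol does not support this, because delays without steroids, short weans, and surgical breaks under 3 weeks (as far as 10.5 goes) are feasible.

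The wording is also softer than a strict reading suggests. Section 8.2.4 is permissive, the exceptions in 7.3.2 are illustrative, and the grade 2 hepatitis steroid is conditional. Grade 2 pneumonitis makes continuation depend on symptoms, not steroid dose. If irAE steroids were meant as an exception to 7.3.2, much of the second conflict would disappear. But the protocol does not say so, and permissive wording leaves the choice to each site.

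A reader might also infer that the conflict holds whichever agent study drug denotes. It does not. Section 10 ties the term to AHCC/placebo, but 8.2.6 speaks of tests every 3 weeks before each administration, which does not suit a daily oral product. If the irAE table means the immunotherapy and 10.5 means AHCC/placebo, delays in the table do not start the 3-week clock.

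On surgery, 10.2 can be read as covering replacement of study treatment and 8.1.2 as covering a perioperative hold. That reading is possible but not stated.

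Finally, the design's grade 3/4 toxicity rates of 0.36 and 0.57 might be taken to size the affected group. They cannot: they cover all grade 3/4 toxicity, not steroid-treated irAEs, and leave out the grade 2 rows.

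**Conclusion.** The point holds in limited form. Three sets of rules need reconciling: the steroid prohibition against the hepatitis and rash rows; steroid-treated delays of about 2 weeks or longer against the 3-week limit when 7.3.2 is applied; and resumption after resection against 10.2 and 10.5. The clearest timing case is grade 3 hepatitis, where the dose is still above 10 mg on day 21 from either end of the 1-2 mg/kg range, given a linear 4-week taper and 50-80 kg. The second conflict also rests on study drug meaning AHCC/placebo in both places.

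The consequence is inconsistent exposure and possibly inconsistent per-protocol membership. A reader might infer bias in the primary comparison. The protocol does not support that: the trial is randomised and double-blind, and the intent-to-treat population counts all enrolled patients whatever their compliance, so the effect shown is at most dilution. Divergence between sites is an inference from the wording; the number of sites and the share of patients given steroids are not stated. Severity: should-fix.

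**What to change.** Reconcile 7.3.2, 8.1.2, 8.2.4, the irAE table, 10.2 and 10.5 so that one rule applies to each situation. The amended text should state:

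- which agent study drug denotes in each of these sections;
- whether steroids given for irAEs are an exception to 7.3.2;
- whether the limit in 10.5 applies to holds for irAEs and for surgery;
- which taper wording governs where 8.2.4 and a table row differ;
- whether surgery counts as an interruption or a discontinuation.

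The clinical content of each rule is for the investigators to decide. Record the reason, start date and end date of every interruption, so that exposure can be described by arm.

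The cost is amendment wording and the data fields for interruptions. No extra visits or patients are needed.

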### 11. Statistical consideration

- 11.1 The primary endpoint is ORR in AHCC arm compared to placebo arm. The secondary endpoints include, incidence and severity of adverse events according to CTCAE version 4, progression-free survival and overall survival.
- 11.2 Exploratory endpoints will include correlation of treatment response (tumor shrinkage, objective response rate, etc.) with immune biomarkers in subjects' samples from tumor tissue and peripheral blood.
- 11.3 We simultaneously monitor efficacy and safety endpoints using the 2-arm Bayesian optimal phase 2 (BOP2) design (Zhao et al., 2020).
- 11.3.1 Specifically, let n denote the interim sample size and N denote the maximum sample size. Let E and C denote the experimental arm and the control arm, respectively. For arm t, t = E, C, let  $Y_{eff,t}$  and  $Y_{tox,t}$  respectively denote the efficacy and toxic endpoints, with  $Y_{eff,t} = 1$  and  $Y_{tox,t} = 1$  respectively indicating that patients experience efficacy and toxicity. We assume that the joint distribution of  $\left(Y_{eff,t}, Y_{tox,t}\right)$  follows a multinomial distribution with four elementary

the joint distribution of  $(1_{eff,t},1_{tox,t})$  follows a martinormal distribution with four elementary

outcomes:  $\left(Y_{eff,t},Y_{tox,t}\right)$  = (1, 1), (1, 0), (0, 1) and (0, 0). Let  $\mathbf{p_t} = \left(P_{11,t},P_{10,t},P_{01,t},P_{00,t}\right)$ 

denote the probabilities of observing the four outcomes, and let  $p_{eff,t} = Pr(Y_{eff,t} = 1)$ ,

$$p_{tox,t} = Pr(Y_{tox,t} = 1)$$
 and  $p_{efftox,t} = Pr(Y_{eff,t} = 1, Y_{tox,t} = 1)$ .

11.3.2 The experimental arm is deemed as unacceptable if  $H_0$ :  $p_{eff,E} \leq p_{eff,C}$  or  $p_{tox,E} > p_{tox,C}$ , i.e., the experimental treatment is inefficacious or overly toxic, with respect to the control. We employ the following Bayesian rule to make a go/no-go decision: (Futility and toxicity stopping) stop enrolling patients and claim that the experimental arm is unacceptable if

$$Pr(p_{eff,E} > p_{eff,C}|data) < \lambda \left(\frac{n}{N}\right)^{\alpha}$$
,

[figure not shown]
OR

$$Pr(p_{tox,E} \leq p_{tox,C}|data) < \lambda \left(\frac{n}{N}\right)^{\alpha}$$
,

where  $\lambda$ =0.68 and  $\alpha$ =0.84 are design parameters optimized to maximize the probability of correctly concluding an efficacious and safe treatment as acceptable when  $p_{eff,E}=0.42$ ,  $p_{tox,E}=0.36$  and  $p_{efftox,E}=0.15$ , while controlling that the probability of incorrectly claiming an inefficacious and toxic treatment, with  $p_{eff,C}=p_{eff,E}=0.27$ ,  $p_{2,C}=p_{2,E}=0.57$  and  $p_{3,C}=p_{3,E}=0.15$ , as acceptable is 10 %. This optimization is performed assuming a vague Dirichlet prior Dir(0.25,0.25,0.25,0.25) for  ${\bf p}$ . The prior is chosen such that it corresponds to a prior effective sample size of 1. The above decision rule leads to the optimal stopping boundaries shown in following tables. The trial stops when either the efficacy endpoint or the toxicity endpoint crosses the stopping boundaries.

[figure not shown]
Optimized stopping boundaries for efficacy endpoint

Interim (no. in control)	Interim (no. in experimental)	No. response (eff) in control	Stop for futility if no. of response in experimental - no. of response in control <=
18	18	0	Never
18	18	1~2	-1
18	18	3~16	-2
18	18	17~18	-1
47	47	0~2	0
47	47	3~12	1
47	47	13~32	2
47	47	33~44	1
47	47	45~47	0

Optimized stopping boundaries for toxicity endpoint

			Stop for unsafety if no. of toxicity in
Interim (no.	Interim (no. in	No. toxicity (tox)	experimental - no. of toxicity in
in control)	experimental)	in control	control >=
18	18	0~1	1
18	18	2~15	2
18	18	16~17	1
18	18	18	Never
47	47	0~3	0
47	47	4~14	-1
47	47	15~34	-2
47	47	35~45	-1
47	47	46~47	0

Based on the above tables and figures, we perform the interim analysis when the number of enrolled patients reaches 36. When the total number of patients reaches the maximum sample size of 94, we reject the null hypothesis and conclude that the experimental arm is acceptable, compared to the control, if both the futility and toxicity stopping boundary are not crossed. Below are the operating characteristics of the design based on 10000 simulations using the BOP2 web application, which is available at http://www.trialdesign.org. Operating characteristics

			Pr(Eff						
			&				Early		
	Pr(Eff	Pr(To	Tox)		Pr(Tox)	Pr(Eff &	Futilit		Avera
	) for	x) for	for	Pr(Eff) for	for	Tox) for	У	Claim	ge
Scena	Contr	Contr	Contr	Experime	Experime	Experime	Stoppi	Promisi	Sampl
rio	ol	ol	ol	ntal	ntal	ntal	ng (%)	ng (%)	e Size
1	0.27	0.57	0.15	0.37	0.47	0.17	23.58	44.40	80.3

- 11.4 The primary endpoint analysis and other secondary endpoints will be based on the intent-to-treat population and per-protocol population, while the safety data will be summarized based on the intent-to-treat population.
  - 11.4.1 Intent-to-treat population refers to all enrolled patients regardless of their compliance with the study drug treatment.
- 11.4.2 Per-protocol population refers to all patients who have received at least 6 weeks (2 cycles) of study medication and received the first scheduled assessment of tumor response.
  - 11.5 Disease stabilization rate (complete response + partial response by RECIST + stable disease by RECIST that last for  $\geq 8$  weeks), objective response rate (complete response + partial

- response by RECIST), and down-staging rate will be calculated with their 95% confidence intervals.
- 11.6 Progression-free survival, time-to-tumor progression, and overall survival will be calculated by the Kaplan-Meier method.
- 11.6.1 Progression-free survival is defined as the duration from the date of the first dose of study drug treatment to the date of documented disease progression or death of any cause.
- 11.6.2 Time-to-tumor progression is defined as the duration from the date of the first dose of study drug treatment to the date of documented tumor progression by imaging studies.
- 11.6.3 Overall survival is defined as the duration from the date of the first dose of study drug treatment to the date of death of any cause.
  - 11.7 The baseline and changes in immune-related biomarkers after study drug treatment will be correlated with the patients' treatment outcome, including disease stabilization, best radiographic response, time to tumor progression, progression-free survival, and overall survival.
  - 11.8 For the endpoint of the safety assessment, the tabulations will count the number of subjects reporting individual adverse events. Incidence of adverse events and serious adverse events will be summarized.
  - 11.9 The demographic features of the subjects will be summarized by descriptive statistics. Comparison between sub-groups, for examples, subjects with vs. without objective tumor response/AFP response/disease stabilization subjects with vs. without surgery after study drug treatment by using Mann-Whitney tests/ one-way ANOVA (continuous variables) or chisquare/Fisher's Exact tests (categorical variables).

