### 1. Abstract

This is a prospective double-blind, randomized, placebo-controlled trial aims to investigate whether add-on of a standardized extract of cultured Lentinula edodes mycelia (AHCC®) can enhance the effect of immunotherapy in cancer patients.

AHCC is a newly developed functional food. In vitro studies have demonstrated that AHCC enhances natural killer cell activity and may serve as a potent biological response modifier for cancer treatment. Previous research involving 269 HCC patients found that 113 patients who took AHCC orally after curative surgery (AHCC group) experienced significantly longer recurrence-free survival (hazard ratio [HR], 0.639; 95% confidence interval [CI], 0.429-0.952; P = 0.0277) and overall survival (HR, 0.421; 95% CI, 0.253-0.701; P = 0.0009) compared to the control group.

This trial will adopt a two-arm Bayesian optimal phase 2 (BOP2) design (Zhao, 2020). The study will simultaneously evaluate efficacy and toxicity. The null hypothesis assumes a true response rate of 0.27 and a grade 3/4 toxicity rate of 0.57, while the alternative hypothesis assumes a true response rate of 0.42 and a grade 3/4 toxicity rate of 0.36. The trial will be conducted in two stages. In the first stage, 36 patients will be recruited and randomized using block randomization with a block size of 4. The study will be terminated early if fewer patients respond in the AHCC group than in the control group or if 2 or more patients in the AHCC group experience grade 3/4 acute toxicity compared to the control group. Otherwise, the second stage will proceed with the recruitment of an additional 58 patients, bringing the total sample size to 94. If, among the 47 patients in the AHCC group, at least 2 more patients respond compared to the control group or if 2 or fewer patients experience grade 3/4 toxicity, we will reject the null hypothesis and conclude that the treatment is promising. This design controls the type I error rate at 0.1 and achieves a power of 0.75. Considering a 5% dropout rate, each group will enroll 49 patients, resulting in a total sample size of 98.

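### The Abstract and Section 11 give different go rules; only Section 11's reproduces the stated error and power, and it demands fewer AHCC toxicities, which 11.1 and H0 do not say

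*Protocol*

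**What the plan says.** Section 11.1: "The primary endpoint is ORR in AHCC arm compared to placebo arm". Adverse events are listed there as secondary.

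Section 11.3.2: H0 is a union, p_eff,E ≤ p_eff,C or p_tox,E > p_tox,C, explained as meaning that "the experimental treatment is inefficacious or overly toxic, with respect to the control". Equal toxicity is not part of it.

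Section 11.3, text and tables: looks at 18 and 47 patients per arm. At the end the trial may "conclude that the experimental arm is acceptable, compared to the control, if both the futility and toxicity stopping boundary are not crossed". The design parameters were chosen by "controlling that the probability of incorrectly claiming an inefficacious and toxic treatment" at 10%, at a point where both arms have response 0.27, toxicity 0.57 and joint probability 0.15.

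Abstract, on the design points: "The null hypothesis assumes a true response rate of 0.27 and a grade 3/4 toxicity rate of 0.57". Both endpoints improve in the other scenario, for which the text reads: "the alternative hypothesis assumes a true response rate of 0.42 and a grade 3/4 toxicity rate of 0.36". On error and power: "This design controls the type I error rate at 0.1 and achieves a power of 0.75". The Abstract's interim rule stops the trial on any shortfall of AHCC responders, or on an AHCC toxicity excess of 2 or more. Its final rule rejects the null if "at least 2 more patients respond compared to the control group or if 2 or fewer patients experience grade 3/4 toxicity".

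**The concern.** The go/no-go rule is what this trial is built to apply, and the protocol states it twice in incompatible forms. The same 94 patients could be called promising under the Abstract and not promising under Section 11. The error and power figures can belong to only one of the two rules.

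There is a second gap inside Section 11. Someone who reads 11.1 and H0 would expect AHCC to pass by raising ORR without raising toxicity. The final toxicity table asks for more: AHCC must show fewer toxic patients than control. That is a superiority demand on an endpoint listed as secondary, and no sentence states it. It also governs what 0.1 and 0.75 mean, because each is fixed at a point where both endpoints move together.

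**Working it through.** **Inputs.** Boundary tables, looks at 18/18 and 47/47, λ = 0.68, α = 0.84 and the Dir(0.25, 0.25, 0.25, 0.25) prior, all from Section 11.3. Control: response 0.27, toxicity 0.57, joint 0.15. Scenarios are written as AHCC response/toxicity/joint. Each was simulated with 1,000,000 trials (18 + 18 patients, then 29 + 29), applying the printed tables. Mean N = 36 + 58 × (1 − early-stop probability).

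**Step 1: reproduce the plan (Section 11 rule).**

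| AHCC scenario | Promising | Stated |
|---|---|---|
| 0.27/0.57/0.15 (joint null) | 0.089 | 0.1 |
| 0.42/0.36/0.15 (joint alternative) | 0.753 | 0.75 |
| 0.37/0.47/0.17 (printed row) | 43.6% | 44.40% |

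For the printed row, early stop is 23.6% (printed 23.58%) and mean N is 80.3 (printed 80.3). The simulated design is therefore the sponsor's.

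**Step 2: the two rules side by side.**

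| | Abstract | Section 11 |
|---|---|---|
| Interim, response | stop if the deficit is 1 or more | stop if the deficit is 2 or more (control 3 to 16 responders) |
| Final, response | at least 2 more | at least 3 more when control has 13 to 32 responders |
| Final, combination | or | both |

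A control count of 13 to 32 out of 47 has probability 0.51 at a rate of 0.27. Early stopping at the joint null is 0.60 under the Abstract and 0.50 under Section 11.

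**Step 3: error and power of the Abstract's rule.** Its toxicity clause can be read in three ways:

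| Reading of '2 or fewer' | Joint null | Joint alternative |
|---|---|---|
| AHCC excess of at most 2 | 0.37 | 0.84 |
| AHCC at least 2 fewer than control | 0.31 | 0.84 |
| at most 2 toxic AHCC patients | 0.21 | 0.78 |

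No reading gives 0.1. Changing only 'or' to 'and', with the clause read as at least 2 fewer, gives about 0.11 and 0.76. That is close to the stated figures, but it is still not the Section 11 rule.

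**Step 4: what the toxicity table demands.** At n = N the cut-off is 0.68 × (47/47)^0.84 = 0.68. Equal counts give Pr(p_tox,E ≤ p_tox,C | data) = 0.50, which fails. With 27 control toxicities (47 × 0.57 ≈ 27), 25 on AHCC gives 0.66 (fail) and 24 gives 0.73 (pass). In the table, a difference of 0, −1 or −2 fails, depending on the row, so AHCC needs at least 1, 2 or 3 fewer. The row needing 3 fewer (control 15 to 34) covers 99% of trials at a control rate of 0.57.

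**Step 5: scenarios in which one endpoint moves (Section 11 rule, independence within the AHCC arm).**

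| AHCC scenario | Early stop | Promising | Mean N | Range over feasible joint probabilities |
|---|---|---|---|---|
| 0.42/0.57/0.24 | 35% | 23% | 73.5 | 0.20 to 0.27 |
| 0.27/0.36/0.10 | 31% | 29% | 75.8 | 0.27 to 0.30 |

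The efficacy rule alone passes 0.31 at equal response rates and 0.82 at 0.42. The toxicity rule alone passes 0.28 at equal toxicity. The figure near 0.1 arises because both rules must be passed when both endpoints are null.

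**The case against.** Several points on the other side have force.

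- **The stated 0.1 and 0.75 are correct at the points the protocol names.** The Abstract defines its null and alternative before quoting them, and Section 11.3 ties the 10% to the same null. The protocol nowhere claims that 0.1 is a maximum over H0. This stands: the figures need a label, not correction.
- **The decision is announced as joint.** The Abstract and 11.3 both say that efficacy and toxicity are evaluated together. This also stands, but neither passage says that AHCC must have fewer toxicities.
- **The strict inequality in H0 is a detail.** Taken alone it changes no boundary. The substance is the demand for fewer events.

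A reader might infer that 0.1 and 0.75 hold only at the two calibration points. That is too strong: response 0.42 with toxicity 0.67, for example, passes in about 5% of trials. The supportable statement is that the design is calibrated at two points and that 0.1 does not bound the error over H0 as printed.

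A reader might also count the 23% both as lost power and as excess error. It cannot be both. Under the printed H0, equal toxicity is acceptable and 23% is a low chance of success. If equal toxicity belongs in H0, 23% is a false-go rate. The documents do not settle which is meant.

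Nor can one infer that single-endpoint scenarios were never examined. The operating-characteristics table shows one row in the text at hand, and others may have been lost in conversion from PDF.

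**Conclusion.** The concern holds in two parts. First, the protocol contains two conflicting go rules, differing in the connective and in the response thresholds. Only Section 11's reproduces the stated figures (0.089 and 0.753); the Abstract's gives 0.21 to 0.37 at the joint null. Second, Section 11 requires an observed reduction in toxicity that neither 11.1 nor H0 states. As a result, 0.1 is not a bound over the printed H0 (about 29% with no ORR gain and toxicity 0.36), and the full ORR gain with unchanged toxicity passes in only about 23% of trials.

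These figures assume control rates of 0.27 and 0.57 with joint probability 0.15, the printed tables, and 47 evaluable patients per arm. The unknown AHCC joint probability moves them only within the ranges shown. This should be fixed before the interim look; it does not invalidate the boundaries or the sample size.

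**What to change.** 1. **Abstract:** replace the interim and final rules with a reference to the Section 11 tables and to the requirement that neither boundary is crossed.
2. **Section 11.1:** state that the go decision rests jointly on ORR and grade 3/4 toxicity, and that the final boundary requires fewer AHCC toxicities than control (at least 3 fewer for 15 to 34 control events).
3. **Section 11.3.2:** reconcile H0 with the toxicity boundary. The sponsor should state whether AHCC must lower toxicity or only not raise it. The present boundaries and calibration fit the former; if that is kept, equal toxicity belongs in H0.
4. **Error and power:** write beside the figures that 0.1 applies at the joint null (0.27 and 0.57 in both arms) and is not a maximum over H0, and that 0.75 applies if ORR is 0.42 and toxicity 0.36. Report the two single-endpoint scenarios from step 5 next to the existing row.

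The cost is wording and two reported scenarios. If the sponsor keeps the present boundaries, neither they nor the sample size change. The downside is that the stated operating characteristics will look less favourable. If the sponsor instead means that AHCC need only not raise toxicity, the toxicity boundary and its calibration would have to be revisited.
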